## 2.2.6 METAGENOMICS, METRANSCRIPTOMICS AND METABOLOMICS DELIVER READOUTS OF MICROBIOME FUNCTION

[figure not shown]
Beyond sequence surveys, whole microbiome DNA and RNA sequencing (metagenomics and metatranscriptomics), together with metabolomics, offer more mechanistic insights, detailing the biochemical functionalities encoded and expressed by the microbiome[65-74]. For example, [name] used metatranscriptomics to reveal how changes in fat absorption in mice impact metabolic pathway expression in the gut microbiome[75]. Further, metabolomics has been transformed by improved technologies for the sensitive detection of metabolites. For example, our group recently revealed significant changes in metabolic pathways involved in lipid and protein metabolism in stunted and severely malnourished children relative to controls[76]. However, the underlying mechanisms explaining how the microbiome affects intestinal and whole-body metabolic function is just starting to be elucidated. **These tools support the functional interrogation of microbiomes to identify microbial pathways that may modulate health and disease.**

---

## 2.2.7 GENDER IMPACTS NUTRITIONAL STATUS AND THE MICROBIOME

It is increasingly apparent that biological sex impacts the gut microbiome, beginning in infancy[77]. While all pregnant individuals have the same biological sex, the experience of being a mother is related to gender roles and identity. Intriguingly, recent research is beginning to reveal how gender-related variables such as socio-economic status, food security, early marriage and maternal empowerment contribute to nutritional status and the development of a healthy intestinal microbiome[78-80]. For example, in low-income settings, maternal empowerment may play a role in improving breastfeeding, diversity and quality of diet in children, setting up the opportunity for a healthy microbiome[81]. Addressing gender roles, specifically with respect to maternal empowerment, has the capacity to directly impact intestinal health in infants.

Conceptual model of maternal socio-economic conditions impact on infant microbiome in Pakistan  
(Adapted from Herd et al., 2017)

**Figure 2: Conceptual Model of Maternal Socio-Economic Conditions Impact on the Infant Microbiome in Pakistan (Adapted from Herd *et al*, 2018[82]).**

### 2.3 RISK AND BENEFITS

This is an observational study. Potential risks to participants include the general risks of giving blood, including: light-headedness, bruising, minor bleeding where the needle is inserted into the arm, pain, and a very low chance of infection. Participants may feel discomfort providing a stool sample, detailed instructions and research staff will be available to provide support. The stool samples are an essential component of the study, and as such are a required component of participation.

Participants may also experience psychological and emotional distress when completing questionnaires and/ or answering questions about their socio-economic status, their health, their infants' health. In addition, some participants may go through postpartum issues that may impact their mental state during the study period. Participants will have the option to leave questions

blank/unanswered if they are uncomfortable, research staff members will be on hand if a participant experience's physiological and/ or emotional distress during a study visit or during study procedures. If this occurs, the study staff members will refer and transport the participant to the government health care facility.

Participants will also have the option to consent to future genetic testing of their serum samples. Genetic information can never be fully de-identified. Although procedures will be put in place to de-identify genetic information, there is a risk that the information gained from genetic research can be linked to participants. While this is very unlikely at this time, rapid scientific advances mean that re-identification may be more likely in the future. There is also a risk of unintentional release of information that could lead to loss of privacy and to possible future discrimination against participants and/ or their biological relatives. The potential future use of genetic information is unknown and therefore not all potential future risks are known. The potential psychological and social risk of participating and receiving genomic information is not fully known at this time. It may be upsetting to learn about genetic causes and medically actionable findings.

There are no direct benefits to participants in the study. However, all participants will be assessed for anemia, and ongoing interaction with the Lady Health Worker Program (LHWs) will be promoted. This provides a small benefit to the study population. All study participants will benefit from receiving appropriate standard of care, which may be better than the average care received in the health system. Participants identified with severe anemia will be referred to nearest public health facility for further evaluation and treatment.

The societal benefits of the proposed study are that it is expected to yield insights into the relationships between prokaryotic and eukaryotic microbes in the gut and their association with maternal health and birth outcomes. The study results are expected to have an impact beyond the study setting. The actual risk of harm caused by a non- interventional trial is expected to be low, and the potential benefits in terms of knowledge generation outweigh the theoretical risks.

### 3 STUDY OBJECTIVES

**Table 4: Study Objectives**

OBJECTIVES	ENDPOINTS	JUSTIFICATION FOR ENDPOINTS
Primary		
To assess if alterations of the microbiota in the maternal gut (dysbiosis) is associated with maternal gestational weight gain.	The primary endpoint will be maternal gestational weight gain (GWG) during pregnancy, measured between the first (10-14 weeks post-conception) and second time point (30-34 weeks post conception).  To monitor microbiome dynamics, 16S and 18S rDNA surveys will be	Weight gain is a key predictor of adverse birth outcomes[83, 84].

OBJECTIVES	ENDPOINTS	JUSTIFICATION FOR ENDPOINTS
	
applied to the maternal stool samples to monitor the bacterial and eukaryotic components of the microbiome.
	
To determine the association between maternal microbiome dysbiosis during pregnancy and birth outcomes, infant growth, nutritional status and health status in the first year of life.	
The specific birth outcomes evaluated will include preterm birth, birth weight, SGA, LGA, head circumference at birth, mortality, morbidity.
 
The specific infant outcomes evaluated will include the following growth and nutritional status parameters; WHO z-scores for weight, length, head circumference and MUAC during the first year.
 
Birth characteristics will be collected, including information on vaginal or cesarean birth (elective, emergency), placental insufficiency and antibiotic usage.
 
Infant morbidity and mortality will be assessed at follow-up visits, with questions regarding care-seeking, hospitalizations and treatments for any morbidity; including antibiotic usage.
 
For the infants an assessment of amount and mode of feeding will be obtained at 3-months, 6-months and 12-months.
 
To monitor microbiome dynamics, 16S and 18S rDNA surveys will be applied to the maternal stool samples to monitor the bacterial and eukaryotic components of the microbiome.
	
This will allow for an examination of the association between the maternal microbiome and birth outcomes.

Secondary		
To link the maternal microbiome to dietary intake, with a focus on calories and macronutrients.	
The maternal participants will complete a 24 hour dietary recall at both time points during pregnancy and at 1-year post-partum.
	
Quantitative measures of nutritional status will provide parameters to better inform microbiome analyses.

OBJECTIVES	ENDPOINTS	JUSTIFICATION FOR ENDPOINTS
	
Food insecurity will be assessed through the use of a food insecurity questionnaire administered at time of recruitment and 3 months post-partum.
 
To assess the quality of the diet through dietary diversity scores.
	
To integrate maternal anthropometric factors, morbidity and mortality with microbiome data to reveal key modulators (microbial taxa and metabolites) of dietary intake during pregnancy and the post-partum period.	
Maternal morbidity will be assessed at follow-up visits, with questions asked about illness or complications during pregnancy, childbirth and the post-partum period, care-seeking, hospitalizations and treatments for any morbidity; including antibiotic usage.
 
Maternal anthropometric measurements will include maternal height, weight, MUAC, and SFT.
	Integration with clinical information will allow for the analysis of microbiome data in the context of patient nutritional status and health outcomes.
To determine the impact of the maternal microbiome during pregnancy, including the exposure to pathogens and parasites, on the development of the infant microbiome.	Maternal and child stool and serum samples will be collected and analyzed for microbiome composition, micronutrients in the serum and stool macronutrients.	These analyses will inform on the role of the maternal microbiome during pregnancy to impact the developing child's microbiome. Our hypothesis is that exposure to pathogens and/or parasites during pregnancy will negatively impact the development of the child's microbiome with downstream consequences for nutrient uptake.
To investigate the maternal microbiome's exposure to pathogens and parasites, and the association with intestinal inflammation.	
The maternal stool samples will be examined for markers of intestinal mass, inflammation, and gut permeability.
 
To monitor the bacterial and eukaryotic components of the microbiome, 16S and 18S rDNA
	These markers will reflect gut health and pathogen challenge.

[figure not shown]

OBJECTIVES	ENDPOINTS	JUSTIFICATION FOR ENDPOINTS
	surveys will be conducted on the stool samples.	
Exploratory		
To explore the role of the maternal gut microbiome during pregnancy and to identify gut community dynamics in pregnant women and how this impacts differences between dietary intake and nutritional status.	To gain more mechanistic insights into the relationship between microbiome function and maternal health and birth outcomes, metatranscriptomics, metabolomics and markers of inflammation will be selectively deployed on the stool samples.	The output of these analyses are concentrations of metabolites that are expected to correlate with pathway expression data; linked to readouts of microbial gene expression detailing biochemical activity and the taxa responsible.
To investigate socio-economic factors; including gender, poverty, exclusion and empowerment, and their influence on the health of a mother's microbiome (assessed by alpha and/or beta diversity, and absence of pathogens).	Participants will answer questionnaires at two time points: baseline and 3-months post-partum. The questionnaire will assess gender related variables focused on five main metrics: perceived maternal self-efficacy, perceived social support, decision making, perceived stress in addition to socio-economic factors, including food and housing insecurity, and demographic data.	The use of previously validated questionnaires within this population, will allow for comparison between the Pakistan and Toronto cohorts, to account for gender related variables that impact maternal and infant gut health.
To explore the role of the human microbiota on nutritional status by performing fecal microbiota transplants in germ free mice and sterile piglets.	The pregnancy rates, birth outcomes, microbiome dynamics, health outcomes, host nutritional status, inflammation and barrier integrity will be collected and assessed.	Exploiting animal models will allow us to define causal interactions between diet, microbiome, pathogen exposure and nutritional status during pregnancy. Through recapitulating patient phenotypes with fecal microbiome transplants, our animal studies will set the stage for developing new therapeutic strategies that promote gut health.

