## 5 STUDY POPULATION

This study will examine young, married women, including newlyweds, 17-24 years of age, living in Matiari District, Pakistan. We will focus on this younger demographic due to our lack of knowledge on the microbiome of young women, and their vulnerability to undernutrition[10]. This will be the first systematic investigation of the impact of the microbiome on nutritional status during pregnancy in young women and directly aligns with global health initiatives focused on this vulnerable cohort.

Upon identification of pregnancy, participants will be screened for eligibility and their pregnancy will be confirmed. If the woman is between 10-14 (+ 2 weeks) post-conception she will be invited to join the study. If she agrees to participate written informed consent will be obtained. Only one woman per household will be eligible to participate in the study.

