### 5.4.1 METHOD FOR MONITORING NEW PREGNANCIES

From the MaPPS trial we found that women typically report their pregnancy to study personnel near the end of the first trimester or start of their second trimester. Field team shall implement multiple strategies to identify new pregnancies:

- 1) The MaPPS study was implemented in the LHW-covered area within the district, and LHWs are required to visit their catchment population once a month. LHWs are required to meet with their respective lady health supervisors (LHSs) in the first week of each month to report pregnancies and share data on several other indicators. Research field staff will join this meeting and get information about new pregnancies.
- 2) Research field staff will get contact numbers of women/families and make regular calls inquiring as to whether they think that they might be pregnant.
- 3) Research field staff will also identify volunteers from within local villages and primary health care facilities to notify them about new pregnancies. A communication card of Rs.100 will be provided to the volunteer against a valid pregnancy notification.
- 4) Research field staff will also employ random check of households and villages and meet with LHWs and volunteers in the field to get information on pregnancies.

Once potential pregnancies are identified by LHWs and volunteers, eligible individuals will be asked by them to provide verbal consent to have a research staff member contact them about the study. If the individual provides this verbal consent to contact, they will be contacted by study personnel at their home to confirm their eligibility. This will include the administration of a pregnancy test to confirm the pregnancy, questions to determine the gestational age (if the gestational age is 16+ weeks the individual will be excluded) and the collection of anthropometric measurements to confirm their BMI is equal to or below 24.9 kg/m^2. The aim will be to recruit participants during the 10-14 week period post-conception, however, women

can be enrolled in the study up to 16 weeks post-conception. Only one participant per household can be enrolled in the study.

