## 9 STATISTICAL CONSIDERATIONS

### 9.1 POWER CALCULATION

The adequacy of the sample size was verified using the ‘pwr’ package (version 1.2-2) in R (version 3.6.1). Calculations were based on the correlation between  $\alpha$ -diversity (Shannon index) and weight gain during pregnancy. Assuming 400 participants are recruited into the study, and a type I error rate of 0.05, there will be 80% power to detect a correlation coefficient ( $r$ )  $>0.14$ . This is conventionally considered a small effect size[109]. Thus, we expect to be powered to reveal significant association between weight gain during pregnancy and diversity. Further, a study of 123 lean and 24 obese individuals, revealed 96% power to detect differences in Bacteroidetes abundance and 80% power for Firmicutes[110], while a cohort of 44 Malawian malnourished children was sufficient to detect significant differences in bacterial  $\alpha$ -diversity in the presence and absence of *Blastocystis*.

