##### **Clinical Variables**

1. Maternal BMI, MUAC and SFT (continuous variables)
2. Maternal gestational weight gain (continuous)
3. Maternal markers of inflammation (continuous)
4. Infant sex
5. Infant morbidity and mortality
6. Infant weight, height, head circumference (continuous)
7. Infant gestational age
8. Infant birth weight, Kg (continuous)
9. Breastfeeding duration (continuous)
10. Maternal age years
11. Maternal use of antibiotics
12. Infant use of antibiotics
13. Maternal calorie and macronutrient intake
14. Maternal incidence of pathobionts
15. Infant incidence of pathobionts

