#### 9.4.1 ADDRESSING THE PRIMARY OBJECTIVES

This study has two primary objectives: 1) To assess if alterations of the microbiota in the maternal gut (dysbiosis) are associated with maternal gestational weight gain; and 2) To determine the association between maternal microbiome dysbiosis during pregnancy and birth outcomes, infant growth, nutritional status and health status in the first year of life.

The first objective will be addressed through the following approaches. First, maternal gut bacteria and eukaryotic profiles will be used to calculate Bray-Curtis dissimilarity metrics between individual samples which will be leveraged in principal co-ordinate analyses to determine the extent samples collected at the first or third trimester, exhibiting similar gestational weight gains, co-cluster. Permutational multivariate analysis of variance (PERMANOVA) tests will assess the degree of overlap between samples exhibiting low gestational weight gain versus samples exhibiting high gestational weight gain. A lack of clustering in the first trimester, followed by clustering of samples on the basis of similar gestational weight gain would indicate that alterations in the maternal microbiota during the course of pregnancy, impacts gestational weight gain. Next, we will attempt to correlate changes in the alpha diversity (as measured by the Shannon and Simpson indices) of the gut microbiome samples between the first and third trimester, with gestational weight gain. A decrease in alpha diversity (indicative of dysbiosis) associated with low gestational weight gain, would again indicate that dysbiosis is associated with maternal weight gain. To examine the influence of individual taxa on gestational weight gain, we will perform bivariate analyses that examine the correlation (Pearson, Spearman) of each taxon with gestational weight gain. Correlations will examine taxon abundance in first and third trimester, in addition to the change in abundance between the two trimesters. The Benjamini-Hochberg procedure will be applied to correct p-values while controlling for false-discovery rates.

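### The primary endpoint is weight gain over a visit interval that can run from 14 to 24 weeks, and neither the endpoint nor the stated primary analyses allow for that interval.

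*Protocol*

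**What the plan says.** Table 4 of the protocol gives the first primary objective this endpoint: "The primary endpoint will be maternal gestational weight gain (GWG) during pregnancy, measured between the first (10-14 weeks post-conception) and second time point", the second time point being 30-34 weeks post-conception. It mentions no rate, reference interval or gestational-age standard. Table 8 (section 9.4) lists gestational weight gain among the clinical variables simply as continuous.

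The first window is wider at enrolment than in Table 4. Section 5 says "If the woman is between 10-14 (+ 2 weeks) post-conception she will be invited to join the study". Section 5.4.1 treats the wider limit as a fallback: "The aim will be to recruit participants during the 10-14 week period post-conception", but women "can be enrolled in the study up to 16 weeks post-conception".

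Section 9.4.1 uses the gain in three stated primary analyses:

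- a PERMANOVA comparing "samples exhibiting low gestational weight gain versus samples exhibiting high gestational weight gain";
- a correlation with diversity change: "we will attempt to correlate changes in the alpha diversity (as measured by the Shannon and Simpson indices") between the first and third trimester;
- bivariate Pearson and Spearman correlations with each taxon, using its abundance in each trimester and its change between them.

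Section 9.1 sizes the study on a simple correlation between the Shannon index and weight gain. With 400 women and a type I error rate of 0.05, "there will be 80% power to detect a correlation coefficient" above 0.14.

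Adjustment is mentioned in three places. Section 8.1.2 names PERMANOVA-S, which can handle confounders. Section 9.3 allows nutritional-status and gender-related covariates where appropriate. The network-fusion and Random Forest models in 9.4.1 draw on all Table 8 variables. None of these names the interval between visits. The nearest item in Table 8 is infant gestational age, which is a different quantity.

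**The concern.** Read as written, the endpoint is a difference between two weights, so part of its spread between women reflects when the visits took place rather than how fast they gained. That part carries no information about the microbiome. It dilutes every correlation with gain, and it moves some women between the low-gain and high-gain groups because of scheduling alone. The sample size statement has no slack to absorb this: it claims 80% power at r = 0.14 with all 400 recruited women analysed.

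A second, smaller issue affects the change-based correlations. Change in diversity and in taxon abundance accrues over the same interval as the gain, so the interval is a possible common cause. Section 2.2.2 describes alpha diversity as falling during pregnancy. A longer interval would then tend to bring more gain and a larger fall, giving a negative bias, against the positive association that section 9.4.1 looks for.

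**Working it through.** **The protocol's own figure.** The formula behind the R routine for correlations is: critical r = sqrt(t²/(t² + n − 2)); power = Φ[(z_r − z_crit)·sqrt(n − 3)] plus a negligible opposite tail, where z_r = atanh(r) + r/(2(n − 1)). With n = 400 and two-sided 0.05, t = 1.966, critical r = 0.0981 and z_crit = 0.0984. At r = 0.14, z_r = 0.1411. Power = Φ(0.0427 × 19.92) = Φ(0.851) = 80.3%. Section 9.1 is reproduced and is not in dispute.

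**Interval limits, from the protocol's windows.**

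- Longest: 34 − 10 = 24 weeks.
- Shortest: 30 − 14 = 16 weeks, or 30 − 16 = 14 with the allowance.
- Ratio of gains at one weekly rate: 24/16 = 1.5, or 24/14 = 1.71.

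**Assumptions (not in the protocol).** Visit times uniform and independent within their windows; mean gain 0.3 to 0.5 kg/week; SD of total gain 3 to 5 kg.

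**Spread of the interval.** Variance of a uniform window = width²/12.

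- Windows 10-14 and 30-34: sqrt(16/12 + 16/12) = 1.63 weeks.
- Windows 10-16 and 30-34: sqrt(36/12 + 16/12) = 2.08 weeks.

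**Share of the variance of gain due to interval, and its effect.** Share = (rate × interval SD)² / (SD of gain)². If diversity correlates 0.14 with interval-adjusted gain, its correlation with total gain is 0.14 × sqrt(1 − share). Power uses the formula above at N = 400.

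| Case | Share | r with total gain | Power | Equivalent N at r = 0.14 |
|---|---|---|---|---|
| Mildest: 0.3 kg/week, SD 5, 10-14 weeks | (0.3 × 1.63)²/25 = 0.010 | 0.139 | 79.9% | 396 |
| Central: 0.4 kg/week, SD 4, 10-14 weeks | (0.4 × 1.63)²/16 = 0.027 | 0.138 | 79.2% | 389 |
| Central, 10-16 weeks | (0.4 × 2.08)²/16 = 0.043 | 0.137 | 78.5% | 383 |
| Worst: 0.5 kg/week, SD 3, 10-16 weeks | (0.5 × 2.08)²/9 = 0.120 | 0.131 | 75.0% | 352 |

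**Group membership.** The protocol does not say how low and high gain are split, so this is illustrative. In simulation, gain was a normally distributed weekly rate times the interval, with the rate SD set to give a total SD of 3 to 5 kg. Under a median split, 3% to 12% of women change group between total and weekly gain. Under thirds, 3% to 15% of the low group and 6% to 18% of the high group change.

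**Change-based correlations, illustration only.** Suppose diversity falls linearly by 0.1 to 0.5 SD on average over the interval. Its correlation with interval runs from −(0.1/20) × 1.63 = −0.008 to −(0.5/19) × 2.08 = −0.055. Multiplying by the correlation of gain with interval (0.10 to 0.35, the square roots of the shares above) gives an induced r of −0.001 to −0.019.

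**Cost of adjusting.** Reducing n by one per covariate at r = 0.14 gives 80.2% with one covariate, 80.1% with two and 80.0% with three.

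**The case against.** The strongest reply is that the protocol fixes only the measurement points. Continuous would fit kilograms per week as well as kilograms, and deriving a change variable, choosing covariates and setting the low/high cut are ordinary SAP matters. For the cut this is right: its absence is missing detail, not an error. For the interval it is not enough. The endpoint and primary analyses are stated here, and following them as written gives total gain without adjustment. The clauses that permit adjustment neither name interval nor list it as a variable.

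The size can fairly be called small. The 1.5-fold and 1.71-fold ratios compare extremes; under uniform visits in the nominal windows, about 94% of intervals lie between 17 and 23 weeks. The worst case treats an enrolment allowance meant as a fallback as routine. In the central case the r detectable with 80% power moves only from 0.1395 to between 0.141 and 0.143. All of this stands and limits the weight of the point.

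The group-change figures depend on splits the protocol does not specify, and the confounding is too small, and in the wrong direction, to create the expected result. Both are illustrations and do not carry the conclusion.

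Finally, dividing by weeks assumes a constant rate of gain, which the protocol does not establish. Anyone who doubts it can keep total gain and adjust for interval.

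**Conclusion.** The concern holds. As defined, the primary endpoint mixes rate of gain with time between visits, and no stated analysis separates them. The interval range of 14 to 24 weeks comes directly from the protocol. The consequences rest on the assumed rate, SD and visit distribution: interval accounts for 1% to 12% of the variance of gain, and power falls by about 0.4 to 5 percentage points (1 to 2 in the central case). That is equivalent to analysing 352 to 396 women instead of 400. Any bias in the change-based correlations is probably very small. This does not threaten the study, but it is an avoidable loss in the primary analysis and should be fixed.

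**What to change.** In Table 4, Table 8 and section 9.4.1, define gestational weight gain as (MV2 weight − MV1 weight) divided by the weeks between the two visits, or keep total gain and include the interval as a covariate. Use the same choice in the correlations and in the low-versus-high PERMANOVA. In the analyses of change in diversity and change in taxon abundance, adjust for interval by partial correlation or regression. It would help to state how low and high gain are split at the same time. A version also adjusted for baseline BMI could be added as a sensitivity analysis but is not required.

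The cost is wording. Weight is already measured at both visits, and the interval needs only the two visit dates, not a gestational-age estimate. Weekly gain uses no degrees of freedom; covariate adjustment costs 0.1 to 0.3 percentage points of power for one to three covariates. Settling this before analysis also removes a later choice between total and weekly gain.
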